## **2. Primary Outcome Variable(s)**

Outcomes will be assessed with a variety of measures of language including naming and picture description. We will contrast performance before and after tDCS using customary statistical techniques (e.g., ANOVA, t-test, etc). We will also perform analyses of MRI data from participants to determine if there is a correlation between measures such as blood flow and atrophy and improvement from tDCS.

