#### ***2.1 Design of tDCS-Only Study***

This is a sham-controlled, full cross-over study design. All subjects with PPA will participate in ten 20-minute tDCS stimulation sessions over the course of 2 weeks using 1.5 mA current. A battery of language tasks will be administered before stimulation sessions, after the 10 sessions, and again at 6 and 12 weeks after the stimulation sessions. The 12-week follow up session will serve as the "baseline" session for the following stimulation sessions. All subjects will also participate in ten 20-minute sham stimulation sessions over the course of 2 weeks. During sham tDCS, a 1.5 mA current will be delivered for approximately 30 seconds at the beginning of the sham session before being extinguished over the course of seconds. Participants will be randomly assigned to receive sham or tDCS stimulation first.

For example, a subject who is assigned to sham stimulation sessions first will first undergo baseline language testing. Then the subject will participate in ten 20-minute sham stimulation sessions over the course of 2 weeks. The subject will go through follow up language testing after the 10th sham stimulation sessions as well as 6 and 12 weeks following the sham stimulation sessions. The 12 week follow up session will serve as the "baseline" for the tDCS stimulation sessions, after which the subject will participate in ten 20-minute tDCS stimulation sessions over the course of 2 weeks, using 1.5 mA current.

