members of a specific category; semantic categories will include tools, animals, and vegetables. Subjects will also be asked to generate words starting with the letters F, A and S. - Repetition, Reading and Writing (single words) will be assessed using the materials developed by the NACC-FTD consortium; subjects are asked to read, write and repeat a series of words controlled for variables known to influence performance such as length, part of speech (noun, verb), imageability (desk vs. fate), age of acquisition, etc. - Elicited Speech Production: Speech samples will be elicited from subjects by presenting a picture book (e.g., Frog story) or scene to be described (Cookie Theft picture from the Boston Diagnostic Aphasia Examination) and asking subjects to describe what they see. Speech production will be scored off-line with respect to fluency (words/minute), grammatically well-formed sentences, mean length of utterance, nouns/100 words, verbs/100 words, phonemic errors, and phonetic errors. Half of subjects will undergo 10 sessions of sham stimulation first and will then undergo 10 sessions of real tDCS stimulation. Half of subjects will undergo 10 sessions of real tDCS stimulation first and will then undergo 10 sessions of sham stimulation. A complete language assessment will be performed before stimulation sessions, after the 10th stimulation session, and 6 and 12 weeks ( $\pm$  1 week) after the completion of stimulation sessions. Real tDCS stimulation will be administered using our standard apparatus (Magstim Eldith with 5x5 cm electrodes) using a current of 1.5 mA. (As a frame of reference, we routinely use 2 mA current in other studies.) The anode will be placed over the left fronto-temporal region of the brain and the cathode over the left occipito-parietal region. During sham stimulation, a 1.5 mA current will be delivered for approximately 10 seconds at the beginning of the sham condition before being extinguished over the course of seconds. As there is some evidence that engaging in the activity that one wishes to enhance while undergoing tDCS improves outcome, all subjects will be shown a children's picture book (e.g., the illustrated version of Cinderella) during the 20 minute period of stimulation and asked to narrate the story, regardless of whether they are in real tDCS stimulation or sham stimulation. Participants assigned to receive sham treatment first will cross over to real tDCS treatment after the 12-week follow up session. Each participant will then receive real tDCS stimulation for 10 sessions over the course of two weeks. The stimulation parameters and testing during treatment will be identical to the previous stimulation sessions, except this time participants will receive real tDCS stimulation instead of sham stimulation. Participants assigned to receive real tDCS stimulation first will cross over to sham stimulation after the 12-week follow up session. Each participant will then receive sham stimulation for 10 sessions over the course of two weeks. The stimulation parameters and language testing during treatment will be identical to the previous stimulation sessions, except this time participants will receive sham stimulation instead of real tDCS

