
stimulation.

Safety and tolerability of the treatment will be assessed in several manners. First, the inclusion/exclusion screening form will be administered both at the initial intake session, as well as at the first session of each 2-week stimulation block. Second, subjects will be queried about new symptoms or adverse effects prior to stimulation on all days when stimulation will be given; should subjects have any concerns, tDCS will not be performed and language will be assessed with fluency tests, naming and a speech sample will be elicited. Third, in the absence of symptoms, language will be assessed at the end of one week of treatment with picture naming, fluency measures and a speech sample will be elicited. Should performance be significantly worse than prior to initiation of treatment, the study will be discontinued; in this event, subjects will be followed on a weekly basis for 4 weeks or until performance returns to baseline (whichever comes first). We propose to use a "significant" change in performance as a cut-off because performance in this condition in the absence of any intervention is quite variable.

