## **2. Statistical Analysis**

Data from each subject will be analyzed using a within-subject design in which change in performance from the baseline testing session to the post-therapy (0, 6, 12 weeks post tDCS) will be compared using t-tests, ANOVAs and other univariate statistics. As it is most relevant to real-world behavior, elicited speech production will serve as the primary endpoint. Depending on our ability to recruit a reasonable sample, group analyses will be also be performed. Finally, we note that high quality imaging will be available for the majority of subjects. Note that we are not proposing to obtain imaging under the auspices of the present study; this data will be available from [name] previously cited protocol. We will perform exploratory analyses in which we attempt to determine if specific imaging parameters (e.g., cortical thickness, degree of atrophy) predict response to tDCS.

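### Group analysis at weeks 0 and 6: change from the block baseline is the only outcome form stated, and adjusting for the baseline difference would save between about 0% and 50% of the variance

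*Combined protocol and SAP*

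**What the plan says.** Study Procedures, 2. Statistical Analysis, takes as its outcome "change in performance from the baseline testing session to the post-therapy (0, 6, 12 weeks post tDCS"), to be "compared using t-tests, ANOVAs and other univariate statistics". The outcome section (2. Primary Outcome Variable(s)) is equally open: "We will contrast performance before and after tDCS using customary statistical techniques (e.g., ANOVA, t-test, etc"). Neither section names baseline as a covariate, and neither rules it out.

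Pooling across subjects is conditional: "Depending on our ability to recruit a reasonable sample, group analyses will be also be performed".

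On design, section 2.1 of Study Design states "This is a sham-controlled, full cross-over study design". The order is balanced (1.1 Procedures for tDCS-Only Study): "Half of subjects will undergo 10 sessions of sham stimulation first and will then undergo 10 sessions of real tDCS stimulation", and the other half the reverse. The second block has no separate baseline visit: "The 12-week follow up session will serve as the 'baseline' session for the following stimulation sessions". Section 1.1 also remarks that "performance in this condition in the absence of any intervention is quite variable".

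The Accrual section says there is no basis for a sample size. Study Duration sections 3.1 and 3.2 expect about 10 subjects a year for about 2 years in the tDCS-only and HD-tDCS+CILT studies, so about 20 each. No accrual figure is given for the svPPA sub-study.

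**The concern.** In a parallel-group trial, subtracting baseline removes stable differences between people. In a two-period cross-over the active-minus-sham contrast has already done that. Subtracting the block baselines as well helps only as far as a subject's baseline shift between blocks predicts the shift in post score. A fixed weight of 1 is right only if the prediction is one for one. Otherwise the subtraction mostly imports measurement error from two more visits.

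At stake is precision in a study of about 20 subjects whose own Risk/Benefit Assessment expects a modest benefit. The data for a better analysis are already being collected. Leaving the role of baseline open also allows the choice between change and adjusted scores to be made after the results are known.

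**Working it through.** **Inputs.** The outcome form, the cross-over design, the 1:1 order and the shared visit are as cited above. N = 20 follows from 10 a year for 2 years; N = 10 is shown as a smaller case. The documents give no SD, reliability, correlation, effect size, alpha or power, so there is no planned figure to reproduce. Every value of r below is an assumption.

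**Notation.** For each subject, D_post is the active-minus-sham difference in post score and D_base the active-minus-sham difference in block baseline. Their variances across subjects within sequence are V_P and V_B, r is their correlation, and b = r·sqrt(V_P/V_B) is the regression slope.

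**Precision without carry-over.**
- Change score: Var(D_post - D_base) = V_P + V_B - 2b·V_B.
- Adjusted: V_P(1-r²) = V_P - b²·V_B.
- Excess of change over adjusted: V_B(1-b)², which is never negative.
- With V_P = V_B = V: change 2V(1-r), adjusted V(1-r²), ratio (1+r)/2, saving (1-r)/2.

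Estimating the slope multiplies the adjusted variance by about 1 + 1/(N-4): 17/16 = 1.0625 at N = 20 and 7/6 = 1.167 at N = 10.

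| r (assumed) | Saving (1-r)/2 | Net, N = 20: 1 - 1.0625(1+r)/2 | Net, N = 10: 1 - 1.167(1+r)/2 |
|---|---|---|---|
| 0 | 50% | 47% | 42% |
| 0.2 | 40% | 36% | 30% |
| 0.4 | 30% | 26% | 18% |
| 0.6 | 20% | 15% | 7% |
| 0.8 | 10% | 4% | -5% |
| 0.9 | 5% | -1% | -11% |

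The net saving vanishes when (1+r)/2 = 16/17 at N = 20 (r = 0.88), or 6/7 at N = 10 (r = 0.71).

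**Which r is plausible.** This r is not the ordinary baseline-to-post correlation. If all visits correlate equally at ρ, the covariance of D_post and D_base is V_Y(ρ - ρ - ρ + ρ) = 0, with V_Y the variance of one score. So r = 0 even when ρ = 0.9. Drift between blocks raises r. I assumed reliability 0.80 to 0.95, a permanent share of 0 to 100% of the reliable variance, weekly autocorrelation 0.90 to 0.98 for the rest, and visits at weeks 0, 2, 8, 14, 16, 22 and 28. Then r runs from 0 to 0.73 at week 0 (saving 50% down to 14%) and from 0 to 0.29 at week 6 (50% down to 35%). Simulation at N = 20 under structures of this kind, without carry-over, left the adjusted estimate unbiased. It showed savings of about 9% to 48% at week 0 and 28% to 46% at week 6.

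**Carry-over at weeks 0 and 6.** Suppose active-first subjects carry an effect c into the block-2 baseline and a fraction f of it remains at the block-2 post visit. Averaged over the two sequences, D_post is shifted by -fc/2 and D_base by -c/2. The bias is therefore (1-f)c/2 for change and (r-f)c/2 for adjusted (equal variances). For an assumed true effect of 0.30, c = 0.15 and r = 0.4:

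| Carry-over | Change | Adjusted |
|---|---|---|
| Persists (f = 1) | 0.300 | 0.255 |
| Halves (f = 0.5) | 0.338 | 0.293 |
| Gone (f = 0) | 0.375 | 0.330 |

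Change is the less biased of the two only when f exceeds (1+r)/2.

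**Week 12.** For an active-first subject the change contrast is (Y14 - Y0) - (Y28 - Y14) = 2·Y14 - Y0 - Y28. With an effect t present at that visit and none carried further, its expectation, leaving out period terms that cancel between sequences, is 2t in active-first and t in sham-first subjects. The average is 1.5t, or 0.45 for t = 0.30. With equal correlation between visits the slope is -0.5 and D_base averages -t/2. The adjusted contrast is then t - 0.25t = 0.75t, or 0.225. Over the wider assumed structures it was 0.22 to 0.27. Both are biased.

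**The case against.** Four points can be made for leaving the plan as it is.

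First, the listed methods are open-ended, so a covariate analysis could fall within them. That stands. A reader might infer that the plan has rejected baseline adjustment, and the text does not say so. What it lacks is a statement of how baseline enters.

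Second, the section starts from each subject's own data and makes group analysis conditional. That stands too. The regression cannot be fitted within one subject, so the point reaches only the group analysis.

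Third, the block-2 baseline is measured after randomisation, so adjusting for it is not automatically safe. This is the strongest objection. If an effect survives 12 weeks and is undiminished two weeks later, change scores are unbiased at week 0 and the adjusted estimate is pulled toward zero: 0.22 to 0.28 for a true 0.30 with c = 0.15. If the carried effect is gone by the post visit, the ranking reverses: 0.36 to 0.38 for change against 0.30 to 0.35 adjusted. Neither form is safe in general, which is why the assumption must be stated and both results shown.

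Fourth, the remark about variable performance is made to justify a cut-off for worsening. It does not separate visit-to-visit noise from real drift, and drift raises r and shrinks the gain. A reader might infer from it a particular loss, such as a third of the precision. A third corresponds to r = 1/3, which nothing in the documents supports, and it is not a ceiling either.

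**Conclusion.** The point holds as one of efficiency and pre-specification for the conditional group analysis at weeks 0 and 6. Without carry-over, the change score is never more precise than the baseline-adjusted contrast, apart from the degree of freedom spent. With equal variances the saving is (1-r)/2, from about 0% to 50%, with r unstated. At N = 20 the net gain disappears near r = 0.88.

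The size carries two further limits. The HD-tDCS+CILT and svPPA sub-studies repeat the baseline before block 1 only, so equal variances are approximate there; the inequality still holds. The svPPA design section (2.2) lists no 6-week visit after the first block, so on that text only week 0 applies to it.

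Two stronger readings are not supported. Change scores do not make the weeks 0 and 6 results invalid, since without carry-over they are unbiased. Nor does adjustment repair every time point: at week 12 both forms fail if the effect lasts that long.

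**What to change.** In Study Procedures, 2. Statistical Analysis:

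- For the group analysis at weeks 0 and 6, regress each subject's active-minus-sham post difference on sequence (which carries the period effect) and the active-minus-sham baseline difference. Code sequence as ±1 and leave the baseline difference uncentred, so that the intercept is the treatment effect. Centring it at its mean would, with balanced sequences, return the unadjusted post difference.
- State the no-carry-over assumption and report the change-score analysis as a sensitivity analysis.
- Where baseline is measured more than once before block 1, state which value or average is used.
- Define week 12 separately, and neither subtract the block-2 baseline there nor use it as a covariate. One option is the between-block difference of the two week-12 scores alone. It is unbiased only if no block-1 effect remains at the block-2 week-12 visit.

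The cost is a wording change and one degree of freedom, with no new visits or data. The downside is a small loss of precision if r is very high or the sample very small, and some bias toward zero at weeks 0 and 6 if carry-over persists undiminished.

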**PROTOCOL ABSTRACT**

The purpose of this study is to treat the language impairment of subjects with Primary Progressive Aphasia using transcranial direct current stimulation (tDCS) and high definition transcranial direct current stimulation (HD-tDCS). PPA is a slowly progressive impairment in language that may be observed in patients with neurodegenerative conditions such as Fronto-temporal dementia or, less commonly, Alzheimer's Disease. tDCS is a form of non-invasive brain stimulation in which very small current (here, 1.5 mA) is applied to the scalp. tDCS will be administered in ten 20 minute sessions over the course of two weeks. Language function will be assessed before, after 1 week of treatment, after 2 weeks of treatment and at 6 and 12 weeks after completion of tDCS. In a sub-study under this protocol, we will pair HD-tDCS with Constraint-Induced Language Therapy (CILT), which preliminary evidence has shown may be a useful speech therapy for individuals with PPA. In this sub-study, we will investigate whether HD-tDCS can enhance the potential benefits of speech therapy (usually very modest in PPA).

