## ***2.2 Design for tDCS with svPPA Sub-study***

For the tDCS with svPPA sub-study, we will also conduct a sham-controlled, full cross-over design. Participants will undergo a battery of cognitive and language testing before treatment. Participants will be pseudo-randomly assigned to two groups, A & B. Group A will receive sham stimulation first, while group B will receive active stimulation first. Groups will be stratified by severity of global cognitive impairment as indexed by performance on the Montreal Cognitive Assessment.

All subjects will participate in ten 20 minute tDCS stimulation sessions over the course of 2 weeks using 2 mA current. The battery of tasks will be administered before stimulation sessions, after the 10 sessions, and again at 12 weeks after the stimulation sessions. The 12-week follow up session will serve as the "baseline" session for the following stimulation sessions. All subjects will also participate in ten 20-minute sham stimulation sessions over the course of 2 weeks. During sham tDCS, a 2 mA current will be delivered for approximately 30 seconds at the beginning of the sham session before being extinguished over the course of seconds. Participants will be randomly assigned to receive sham or tDCS stimulation first. After the second treatment/sham period, the cognitive/language tasks will be administered again, and then additionally at 6 and 12 week follow-up sessions.

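### The cross-over analysis specifies no period term, so any block-1/block-2 shift in change scores costs power and, if the two orders are unequal in size, biases the estimate

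*Combined protocol and SAP*

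**What the plan says.** The tDCS-only component is described thus: "This is a sham-controlled, full cross-over study design" (Study Design, 2.1). The HD-tDCS+CILT and svPPA sub-studies take the same form (the two sections numbered 2.2). On order, the tDCS-only design says "Participants will be randomly assigned to receive sham or tDCS stimulation first", and the procedures state the intended ratio: "Half of subjects will undergo 10 sessions of sham stimulation first and will then undergo 10 sessions of real tDCS stimulation" (Study Procedures, 1.1; repeated in 1.2 and 1.3). In svPPA, assignment is pseudo-random and "Groups will be stratified by severity of global cognitive impairment as indexed by performance on the Montreal Cognitive Assessment". In the tDCS-only and svPPA designs, the 12-week follow-up of the first block doubles as the baseline of the second, and the CILT design adopts the tDCS-only scheme.

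One paragraph covers the analysis of all three (Study Procedures, 2. Statistical Analysis): "Data from each subject will be analyzed using a within-subject design", with changes from baseline that "will be compared using t-tests, ANOVAs and other univariate statistics". Then: "Depending on our ability to recruit a reasonable sample, group analyses will be also be performed". The outcome section adds only a general reference to customary techniques. Neither place names period or sequence as a model term.

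**The concern.** In a two-period cross-over, each participant's active-minus-sham difference contains the treatment effect plus or minus any difference between the blocks. The protocol gives grounds to expect such a difference:

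- The language battery is repeated through both blocks.
- CILT is repeated, and its stated aim is that participants progress in difficulty (Study Procedures, 1.2).
- In svPPA, items move between vulnerable and mastered lists as training goes on (1.3), so the second block can start from a different item mix.
- The disease itself progresses: "PPA is a slowly progressive impairment in language".

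An unadjusted paired test puts this shift into the error term. If more people complete one order than the other, part of it also enters the treatment estimate. The comparison at stake is active versus sham, which is the main question of all three components.

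**Working it through.** **Inputs from the documents.** About 10 participants a year for about 2 years (3.1 Study Duration of tDCS-Only Study; the same in 3.2 for HD-tDCS+CILT), so N is about 20. No enrolment figure is given for svPPA. No SD, effect size, alpha or power is stated, so there is no figure of the plan's own to reproduce.

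**Assumptions.** Two-sided alpha 0.05. All effects are in units of the SD of the within-person difference. True effect τ = 0.66, which gives about 80% power at N = 20 with no shift: (1.960 + 0.842)² / 0.66² = 18.0, or about 20 after the small-sample correction. Period shift π = 0.25, 0.5 or 1.0.

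**Which period effects survive.** Let decline be b per week.

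- Change over the two weeks from each block's own baseline is −2b in both blocks, so the difference is 0.
- If both blocks are measured from the initial baseline, block 2 starts 2 + 12 = 14 weeks later. The changes are −2b and −16b, and they differ by −14b.

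The analysis section refers to the baseline session without saying which one. Practice, therapy learning, non-constant decline and floor or ceiling effects remain in either case.

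**Model.** D = active change − sham change. For sham-first, D = τ + π + e. For active-first, D = τ − π + e. SD(e) = 1.

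- Bias of the unadjusted mean of D = π × (n sham-first − n active-first) / N.
- With equal orders, the expected estimated variance of D is 1 + π² × N/(N − 1), against a true value of 1. At N = 20 the SE is inflated by √1.066 = 1.03, √1.263 = 1.12 and √2.053 = 1.43. The ratio of simulated mean SEs at π = 1.0 is 1.44.
- The period-adjusted estimate averages the two sequence means of D, with the pooled within-sequence SD and N − 2 df.

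**Results (200,000 simulated trials per cell), unadjusted paired t-test.**

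| Split | Quantity | π = 0.25 | π = 0.5 | π = 1.0 |
|---|---|---|---|---|
| 10:10 | Bias | 0 | 0 | 0 |
| 10:10 | SE too wide by | 3% | 12% | 43–44% |
| 10:10 | Type I error | 4.5% | 3.0% | 0.6% |
| 10:10 | Power | 78% | 72% | about 50% |
| 12:8 | Bias (0.2π) | 0.05 | 0.10 | 0.20 |
| 12:8 | Type I error | below 5% | 4.6% | below 5% |
| 14:6 | Bias (0.4π) | 0.10 | 0.20 | 0.40 |
| 14:6 | Type I error | about 6% | about 10% | about 16% |

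The bias can run for or against stimulation, depending on which order is larger and on the sign of π.

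**With a period term**, at every π: bias 0, type I error about 5%, and power 79.8% (10:10), 78.1% (12:8) and 72.6% (14:6).

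**How likely is imbalance?** The allocation method is not stated. Under simple randomisation of 20, Binomial(20, 0.5) gives exactly 10:10 with probability 18%, 12:8 or worse 50%, and 14:6 or worse 12%. Averaged over all splits, the unadjusted test has mean bias of about 0, type I error of about 5%, and power of about 77.5%, 70.5% and 50%.

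**Single participants.** With one person there is one order, so D estimates τ + π or τ − π. Period and treatment are fully aliased, and no added term separates them.

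**The case against.** The strongest reply is that the design already handles decline. The 12-week visit is the baseline for the second block, so steady deterioration drops out of block-specific change. This stands. A reader might infer that ordinary decline will be credited to, or taken from, stimulation; for constant decline measured from each block's own baseline, that is wrong. It leaves the other sources of a shift untouched, and the analysis section does not say that the block-specific baseline is the one used.

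Second, the plan does not exclude a period term, since its ANOVAs are undefined. That is also right: the accurate statement is that none is specified. Nor does the plan name a paired test of active minus sham, so the figures above describe a natural reading of it.

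Third, the larger shifts are assumed, and PPA progresses slowly. At a shift of 0.25 with equal orders, the loss is about 2 points of power. A reader might also infer a general excess of false positives. The calculation does not support that: with equal orders the test is conservative, at 12:8 type I error is not inflated, and over simple randomisation it averages about 5%. The inflation is conditional on a split such as 14:6.

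Fourth, three further inferences lack support in the documents: that order was randomised because the blocks were expected to differ, that Montreal Cognitive Assessment severity predicts the rate of decline, and that N = 20 or the binomial probabilities apply to svPPA, whose allocation is stratified.

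**Conclusion.** The point holds as an omission that is cheap to repair. For whatever group analysis is run, the plan specifies nothing to remove a block-1/block-2 shift. For the per-participant analysis that it puts first, no term can do so.

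Under the stated assumptions, the cost ranges from about 2 points of power (shift 0.25, equal orders) to about 30 points (shift 1.0). When the orders are unequal, the estimate is also biased by the shift times the difference in sequence sizes over N. The size of the shift is unknown from the documents, and the whole result is conditional on its being non-zero.

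This should be fixed before the data are analysed. It does not invalidate the cross-over, and with the intended equal split the error is on the conservative side.

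**What to change.** In Study Procedures, 2. Statistical Analysis:

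- Make active versus sham a group-level comparison in a linear mixed model of change from each block's own baseline, with fixed treatment and period and a random participant effect. With two blocks, this is equivalent to comparing period differences between the two sequences.
- Say explicitly that the second block's baseline is the 12-week visit.
- Describe single-participant results as descriptive.
- In svPPA, the cognitive-severity stratum already used for allocation may be added. A stratum-by-period term is not needed.

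In the design sections, state that order is assigned from a list in permuted blocks, so that the intended half-and-half split is actually delivered. Dropout can still unbalance it, which is a further reason for the period term.

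Cost: some wording, a blocked list and one degree of freedom; no new data. If there is in truth no period effect, power falls from 80.0% to 79.8% at 10:10 and from 80.0% to 78.1% at 12:8. At 14:6 it would fall to 72.6%, which is why blocking belongs with the model. The period term does not remove carry-over from the first block, which is a separate matter.
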